#### 4.0 STAGING CRITERIA

##### DEFINITION OF TNM (AJCC Seventh Edition, 2010)

##### Primary Tumor (T)

TX	Primary tumor cannot be assessed
T0	No evidence of primary tumor
T1	Tumor 7 cm or less in greatest dimension, limited to the kidney
T1a	Tumor 4 cm or less in greatest dimension, limited to the kidney
T1b	Tumor more than 4 cm but not more than 7 cm in greatest dimension, limited to the kidney
T2	Tumor more than 7 cm in greatest dimension, limited to the kidney
T2a	Tumor more than 7 cm but less than or equal to 10 cm in greatest dimension, limited to the kidney
T2b	Tumor more than 10 cm, limited to the kidney

T3	Tumor extends into major veins or perinephric tissues, but not into the ipsilateral adrenal gland and not beyond Gerota's Fascia
T3a	Tumor grossly extends into the renal vein or its segmental (muscle containing) branches, or tumor invades perirenal and/or renal sinus fat but not beyond Gerota's Fascia
T3b	Tumor grossly extends into the vena cava below the diaphragm
T3c	Tumor grossly extends into the vena cava above the diaphragm or invades the wall of the vena cava
T4	Tumor invades beyond Gerota's Fascia (including contiguous extension into the ipsilateral adrenal gland). NOTE: Non-contiguous adrenal lesion is considered M1 disease and not eligible for protocol participation.

### **Regional Lymph Nodes (N)**

NX	Regional lymph nodes cannot be assessed
N0	No regional lymph node metastasis
N1	Metastasis in regional lymph node(s)

### **Distant Metastasis (M)**

M0	No distant metastasis
----	-----------------------

### **HISTOLOGIC GRADE (G)**

GX	Grade cannot be assessed
G1	Well differentiated
G2	Moderately differentiated
G3	Poorly differentiated
G4	Undifferentiated

### **PATHOLOGIC STAGE**

#### **Intermediate High-Risk Group**

pT1b	G3-4, N0 (or pNX where clinically N0), M0
pT2a-b	G1-2, N0 (or pNX where clinically N0), M0
pT2 a-b	G3-4, N0 (or pNX where clinically N0), M0
pT3a	G1-2, N0 (or pNX where clinically N0), M0

Microvascular invasion of the renal vein of pT1a-pT3a (as long as pT3a is Grade 1-2) N0 (or pNX where clinically N0) M0

#### **Very High Risk Group**

pT3a	G3-4, N0 (or pNX where clinically N0), M0
pT3b-c	G any, N0 (or pNX where clinically N0), M0
pT4	G any, N0 (or pNX where clinically N0), M0
pT any	G any, N+ (fully resected), M0

Microvascular invasion of the renal vein with above other characteristics

## **5.0 ELIGIBILITY CRITERIA**

Each of the criteria in the following section must be met in order for a patient to be considered eligible for registration. Use the spaces provided to confirm a patient's eligibility. For each criterion requiring test results and dates, please record this information on the **S0931** Prestudy Form and submit to the Data

Operations Center in Seattle (see [Section 14.0](#)). Any potential eligibility issues should be addressed to the Data Operations Center in Seattle at [[contact]](mailto:[contact]) or [name] prior to registration.

In calculating days of tests and measurements, the day a test or measurement is done is considered Day 0. Therefore, if a test is done on a Monday, the Monday 2 weeks later would be considered Day 14. This allows for efficient patient scheduling without exceeding the guidelines. **If Day 14, 28, 42, or 84 falls on a weekend or holiday, the limit may be extended to the next working day.**

#### 5.1 Disease Related Criteria

- a. Patients must have histologically or cytologically confirmed renal cell carcinoma (clear cell or non-clear cell allowed, but collecting duct or medullary carcinomas excluded). Patients must be considered pathologically either Intermediate High Risk or Very High Risk as defined in [Section 4.0](#). Patients must not have a history of distant metastases. Patients with microvascular invasion of the renal vein of any grade or stage (as long as M0) are also eligible.
- b. Patients must have undergone a full surgical resection (radical nephrectomy or partial nephrectomy), including removal of all clinically positive nodes. Surgical margins must be negative. Patients with positive renal vein margins are eligible unless there is invasion of the renal vein **wall** at the margin (provided no other margins are positive). Patients must plan to start study drug within 84 days after the date of full surgical resection. Patients must have recovered from any surgical related complications.
- c. Patients with bilateral renal tumors are eligible provided both tumors have undergone full surgical resection and at least one of the tumors meets all eligibility criteria in Sections 5.1a-b. Patients must plan to start study drug within 84 days after the date of the resection of the first tumor.
- d. Patients must not have any evidence of residual or metastatic renal cell cancer on CT scan of the chest, abdomen, and pelvis, all with oral and IV contrast after nephrectomy and within a maximum of 28 days prior to registration. An MRI scan of the abdomen/pelvis with gadolinium and a non-contrast CT of the chest is an acceptable imaging alternative. Non-contrast CT of the chest/abdomen/pelvis should only be performed if, in the opinion of the investigator, it is in the best medical interest of the patient to not receive IV contrast of any form. NOTE: PET/CT is not an acceptable imaging alternative. Patients who display subcentimeter pulmonary nodules (by CT scan) that are non-specific and considered unlikely to represent metastatic disease by the treating investigator will be considered eligible.

#### 5.2 Prior Therapy Criteria

- a. Patients must not have received any prior anti-cancer therapy (except for radical or partial nephrectomy noted above) for renal cell carcinoma, including systemic therapy in the adjuvant or neoadjuvant setting, immunotherapy, investigational therapy, surgical metastaticity, or radiation therapy.
- b. Patients must not be planning to receive other anti-cancer agents including investigational agents while on protocol treatment.
- c. Patients must not be receiving chronic, systemic treatment with corticosteroids or other immunosuppressive agent. Topical or inhaled corticosteroids are allowed.
- d. Patients must not have received immunization with an attenuated live vaccine within seven days prior to registration nor have plans to receive such vaccination while on protocol treatment.

- e. Patients must not be taking, nor plan to take while on protocol treatment, strong CYP3A4 inhibitors, (e.g. ketoconazole, itraconazole, voriconazole, posaconazole, fluvoxamine, nefazodone, nelfinavir, ritonavir) and/or strong CYP3A4 inducers (e.g. phenytoin, rifampin, rifabutin) within 14 days prior to randomization. (Moderate inhibitors or inducers of isoenzyme CYP3A4 should be avoided, but if necessary can be used with caution. See [Section 7.1c.](#))

### 5.3 Clinical/Laboratory Criteria

- a. Patients must have a complete physical examination and medical history within 28 days prior to registration.
- b. Patients must not have any Grade III/IV cardiac disease as defined by the New York Heart Association Criteria (i.e., patients with cardiac disease resulting in marked limitation of physical activity or resulting in inability to carry on any physical activity without discomfort), unstable angina pectoris, myocardial infarction within 6 months, or serious uncontrolled cardiac arrhythmia. See [Appendix 18.1.](#)
- c. Patients must not have any known uncontrolled underlying pulmonary disease (e.g. FEV1 or DLCO 50% or less of predicted **OR** O2 saturation 88% or less at rest on room air).
- d. Patients must not have any known hypersensitivity to everolimus or other rapamycins (sirolimus, temsirolimus) or to its excipients.
- e. Patients must have absolute neutrophil count (ANC)  $\geq 1,500/\text{mcl}$ , platelet count  $\geq 100,000/\text{mcl}$  and hemoglobin  $\geq 9.0 \text{ g/dl}$  obtained within 28 days prior to registration.
- f. Patients must have serum creatinine  $\leq 2.0 \times$  upper limit of normal (ULN) or calculated creatinine clearance (CrCl)  $\geq 30\text{mL}/\text{min}$  obtained within 28 days prior to registration.

$$\text{Calculated creatinine clearance} = \frac{(140 - \text{age}) \times \text{wt (kg)} \times 0.85 \text{ (if female)}}{72 \times \text{creatinine (mg/dl)}}$$

- g. Patients must have bilirubin  $\leq 1.5 \times$  ULN, and SGOT and SGPT  $\leq 2.5 \times$  ULN obtained within 28 days prior to registration.
- h. Patients must NOT have liver disease such as cirrhosis or severe hepatic impairment (Child-Pugh Class C). NOTE: A detailed assessment of Hepatitis B/C medical history and risk factors must be done at screening for all patients. HBV and HCV testing are required at screening for all patients with a positive medical history based on risk factors and/or confirmation of prior HBV/HCV infection. (See [Section 9.0](#) for testing information and [Section 8.6](#) for management of patients with positive testing.)
- i. Patients must not have a known history of HIV seropositivity.
- j. Patients must not have uncontrolled hyperlipidemia (fasting serum cholesterol  $>300 \text{ mg/dL}$  AND fasting triglycerides  $> 2.5 \times$  ULN) obtained within 28 days prior to registration. Optimal lipid control must be achieved before registration and monitored during protocol treatment (see [Section 8.4b.](#))
- k. Patients must not have uncontrolled diabetes mellitus (defined by fasting serum glucose  $> 1.5 \times$  ULN) obtained within 28 days prior to registration. Optimal

glucose control must be achieved before registration and monitored during protocol treatment (see [Section 8.4b](#)).

- l. Patients must be able to take oral medications. Patient may not have any impairment of gastrointestinal function or gastrointestinal disease that may significantly alter the absorption of everolimus (e.g. ulcerative disease, uncontrolled nausea, vomiting, diarrhea, malabsorption syndrome or small bowel resection).
- m. Patients must have a Zubrod Performance Status of 0 or 1 (see [Section 10.3](#)).
- n. All patients must be 18 years of age or older.
- o. No other prior malignancy is allowed except for the following: adequately treated basal cell or squamous cell skin cancer, in situ cervical cancer, adequately treated Stage I or II cancer from which the patient is currently in complete remission, or any other cancer from which the patient has been disease-free for 5 years.
- p. Patients must not be pregnant or nursing due to animal studies that have shown reproductive toxicity effects. Women/men of reproductive potential must have agreed to use an effective contraceptive method during protocol treatment and up to 8 weeks after ending protocol treatment. A woman is considered to be of "reproductive potential" if she has had menses at any time in the preceding 12 consecutive months. In addition to routine contraceptive methods, "effective contraception" also includes heterosexual celibacy and surgery intended to prevent pregnancy (or with a side-effect of pregnancy prevention) defined as a hysterectomy, bilateral oophorectomy or bilateral tubal ligation. However, if at any point a previously celibate patient chooses to become heterosexually active during the time period for use of contraceptive measures outlined in the protocol, he/she is responsible for beginning contraceptive measures.

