Grade 3 febrile neutropenia (not life-threatening)	Interrupt everolimus until resolution of fever and neutropenia to Grade $\leq 1$ . Hold further everolimus until the ANC $\geq 1,500/mm^3$ and fever has resolved. Then resume everolimus at one lower dose level. If febrile neutropenia recurs, discontinue everolimus.
Grade 4 febrile neutropenia (life-threatening)	Discontinue everolimus.

\* Grade 2-3 hyperlipidemia (hypercholesterolemia and/or hypertriglyceridemia) should be managed using medical therapies (see [Section 8.4b](#)).

If a patient requires a dose delay of > 21 days for pneumonitis or > 28 days for any other reason from the intended day of the next scheduled dose, then the patient must be removed from the protocol treatment.

a. Hematological Toxicity

No dose adjustments are recommended for anemia. The treating physician may hold everolimus for anemia if it is felt to be in the best interest of the patient. Aranesp (darbepoetin alfa) and Procrit (epoetin alfa) are not indicated for anemia. If patient does not recover after 28 days of holding drug then the patient must be removed from treatment.

Growth factors (e.g. G-CSF, GM-CSF, erythropoietin, platelet growth factors, etc.) are not to be administered prophylactically but may be prescribed by the treating physician for rescue from severe hematologic events.

b. Hyperlipidemia and Hyperglycemia

Treatment of hyperlipidemia should take into account the pre-treatment status and dietary habits. Blood tests to monitor hyperlipidemia must be taken in the fasting state. Grade 2 or greater hypercholesterolemia (> 300 mg/dL or 7.75 mmol/L) or Grade 2 or greater hypertriglyceridemia (> 300 mg/dL - 500 mg/dL; >3.42 mmol/L- 5.7 mmol/L) should be treated with a 3-hydroxy-3-methyl-glutaryl (HMG)-CoA reductase inhibitor (e.g., atorvastatin, pravastatin) or appropriate lipid-lowering medication, in addition to diet. Patients should be monitored clinically and through serum biochemistry for the development of rhabdomyolysis and other adverse events as required in the product label/data sheets for HMG-CoA reductase inhibitors.

Note: Concomitant therapy with fibrates and an HMG-CoA reductase inhibitor is associated with an increased risk of a rare but serious skeletal muscle toxicity manifested by rhabdomyolysis, markedly elevated creatine phosphokinase (CPK) levels and myoglobinuria, acute renal failure and sometimes death. The risk

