versus benefit of using this therapy should be determined for individual patients based on their risk of cardiovascular complications of hyperlipidemia.

Grade 3 hyperglycemia has been observed in patients receiving everolimus therapy. The fasting state of patients should be verified when interpreting results. It is suggested that optimal glucose control should be achieved before starting a patient on everolimus and should be monitored during everolimus therapy.

c. Pneumonitis

Pneumonitis is a recognized adverse effect of rapamycins (sirolimus, temsirolimus, and everolimus). Numerous case reports in the literature suggest that rapamycin-associated pneumonitis is relatively unaggressive, limited in extent, and reversible upon drug discontinuation. The term 'pneumonitis' is used here to describe non-infectious, non-malignant infiltration in the lungs which is evident radiologically. More precise diagnosis should follow histocytological examination following lung biopsy, generally during bronchoscopy which may or may not be symptomatic.

Both asymptomatic and symptomatic non-infectious pneumonitis have been noted in patients receiving everolimus. A diagnosis of non-infectious pneumonitis should be considered in patients presenting with non-specific respiratory signs and symptoms such as hypoxia, pleural effusion, cough or dyspnea, and in whom infectious, neoplastic and other non medical causes have been excluded by means of appropriate investigations. Patients should be advised to report promptly any new or worsening respiratory symptoms.

In order to monitor for asymptomatic non-infectious pneumonitis, the regularly scheduled chest CTs for disease surveillance should be assessed for evidence of pneumonitis during protocol treatment. Additional chest CT scans may be performed, when clinically necessary. If non-infectious pneumonitis develops, a consultation with a pulmonologist should be considered.

Management of Non-Infectious Pneumonitis

Worst Grade Pneumonitis	Required Investigations	Management of Pneumonitis	Everolimus Dose Adjustment
Grade 1	CT scans with lung windows and pulmonary function testing including: spirometry, DLCO, and room air O 2 saturation at rest. Repeat chest x-ray/CT scan every 2 Cycles until return to baseline.	No specific therapy is required	Administer same dose of everolimus.

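### Section 5.3j calls lipids uncontrolled only when cholesterol and triglycerides are both high, while Section 8.4b acts on either alone, so lipid eligibility is ambiguous and lipid adverse events lack a baseline reference (minor)

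*Combined protocol and SAP*

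**What the plan says.** **Entry.** Section 5.3j opens "Patients must not have uncontrolled hyperlipidemia (fasting serum cholesterol", sets that limit at 300 mg/dL, and continues "AND fasting triglycerides" with a limit of 2.5 times ULN. Both must be exceeded. It then adds "Optimal lipid control must be achieved before registration and monitored during protocol treatment" and points to Section 8.4b. It gives no figure for that control.

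**On treatment.** Section 8.4b joins the two abnormalities with *or*: "Grade 2 or greater hypercholesterolemia (> 300 mg/dL or 7.75 mmol/L) or Grade 2 or greater hypertriglyceridemia (> 300 mg/dL - 500 mg/dL". Either one should be treated with a statin "or appropriate lipid-lowering medication, in addition to diet". A footnote to the Section 8.4 table says "Grade 2-3 hyperlipidemia (hypercholesterolemia and/or hypertriglyceridemia) should be managed using medical therapies", and the Grade 2 and Grade 3 non-hematological rows exempt hyperlipidemia from dose modification.

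**Analysis.** Comparing toxicity between arms is a secondary objective (Section 1.2b). Section 11.5 tabulates Grade 2-4 high cholesterol (10%) and hypertriglyceridemia (27%) on everolimus. It relates adverse events to blood concentration by logistic regression, adjusted for the stratification factors, age, sex and race. Neither Section 11.3 nor Section 11.5 says how an abnormality already present at entry is handled. The Section 9.0 calendar requires fasting cholesterol and triglycerides prestudy and again from Week 7.

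**The concern.** Section 5.3j sends the reader to Section 8.4b for lipid control, but the two sections measure control differently. The connector differs, and so does the triglyceride scale (a multiple of the local ULN against a fixed value). The same prestudy result can fall outside the entry definition of uncontrolled and still meet the level at which 8.4b calls for treatment.

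Two things are at stake. First, sites could reach different eligibility decisions on identical results, although Section 13.5 allows no exceptions to the eligibility requirements. Second, a patient who enters at Grade 2 could be counted among the Grade 2-4 lipid events without any change on treatment. That would raise the absolute rates. It would also add events unrelated to drug level, which pulls the trough-level association toward the null.

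**Working it through.** This is a comparison of rules; the plan gives no figure to reproduce.

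**Inputs**
- Section 5.3j: uncontrolled if cholesterol > 300 mg/dL **and** triglycerides > 2.5 × ULN.
- Section 8.4b: treat if cholesterol > 300 mg/dL **or** triglycerides > 300 mg/dL.
- Triglyceride ULN: not in the documents. Assumed range 120 to 200 mg/dL.

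**Step 1, triglyceride limits on one scale.** 2.5 × 120 = 300; 2.5 × 150 = 375; 2.5 × 175 = 437.5; 2.5 × 200 = 500 mg/dL. The limits coincide only at ULN = 300 / 2.5 = 120 mg/dL. Above that, the 5.3j limit is the higher of the two.

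**Step 2, test values (mg/dL).**

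| Cholesterol | Triglycerides | 5.3j definition met? | 8.4b threshold met? |
|---|---|---|---|
| 320 | 100 | No, at every assumed ULN | Yes, cholesterol |
| 250 | 310 | No, at every assumed ULN | Yes, triglycerides |
| 250 | 340 | No, at every assumed ULN | Yes, triglycerides |
| 320 | 340 | No at ULN 150, 175 and 200; yes at 120 | Yes, both |

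**Step 3, separate the two causes.** The first row needs no assumption about ULN: the cholesterol limit is 300 mg/dL in both sections, so the mismatch comes from the connector alone. The triglyceride scale is a second, independent cause. With cholesterol 250 and triglycerides 310 or 340, and ULN 150 to 200, the patient would fall outside the 5.3j definition whichever connector it used. Addressing the connector alone would therefore not make the sections agree.

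**Step 4, does the control sentence settle it?** It is mandatory, since Section 5.0 requires every criterion to be met. Read strictly, it could bar all four patients. Read with the only numbers beside it, it bars none of the first three. The text does not say which reading applies.

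**Step 5, reach into the analysis.** A lipid value already at Grade 2 before the first dose cannot be caused by the drug. If it is counted as an event, it enters the Section 11.5 model regardless of concentration. Prestudy lipids are not among that model's listed covariates.

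**The case against.** The strongest reply is that an entry limit and an on-treatment action level need not coincide. Section 8.4b tells physicians to consider lipid status before treatment, so it anticipates abnormal baseline values, and Grade 2-3 hyperlipidemia leads to medical management with no dose change. That stands as an answer to any charge of a dosing conflict. It does not supply a value for optimal control, and 5.3j names 8.4b as its reference.

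Several stronger readings are tempting, and the documents do not support them:

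- **That such patients are plainly eligible.** The control sentence may exclude them. The text supports ambiguity only.
- **That a large part of the 10% and 27% rates was present at entry.** The documents give no distribution of prestudy lipids. They also do not say that unchanged pre-existing values are recorded as adverse events.
- **That an isolated extreme value would meet the Grade 4 discontinuation row at the first on-treatment labs.** That row has no hyperlipidemia exemption, but no Grade 4 lipid cut-off appears in the documents. The argument also requires the control sentence to have no force.
- **That the glucose wording conflicts as well.** Section 5.3k makes control before registration mandatory, while 8.4b says "It is suggested that optimal glucose control should be achieved before starting a patient on everolimus". Registration precedes treatment (Section 13.1), so meeting the first satisfies the second.
- **That the comparison between arms is biased.** Treatment is randomized and blinded, so pre-existing cases are expected equally in both arms. They can add noise but do not systematically favor either arm.

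**Conclusion.** The inconsistency is real and minor. Sections 5.3j and 8.4b differ in connector and in triglyceride scale, and the sentence that might bridge them has no value. The cholesterol mismatch rests on no assumption. The triglyceride scale mismatch holds for any ULN above 120 mg/dL, a quantity the documents do not give.

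The effect cannot be sized in patients or events. Recurrence-free survival, its power and its alpha are untouched. The possible consequences are confined to absolute lipid toxicity rates and the lipid trough-level analyses, and only to the extent that values unchanged from baseline are counted as events. Within those analyses the cholesterol endpoint has the least room for dilution: at 10% prevalence, Section 11.5 already gives a minimally detectable odds ratio of 6.5.

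**What to change.** 1. **Reconcile Sections 5.3j and 8.4b.** The sponsor should settle the connector, the triglyceride scale and what optimal lipid control means. No position is taken here on which rule is correct. The December 2020 update in Section 11.2 reports three interim analyses done and counts follow-up from the last accrual, so enrollment appears complete. This step would therefore mainly clarify how the entered population is described. It costs a text clarification.

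2. **Use baseline in the lipid analyses.** In Section 11.3, alongside the planned tabulation, show cholesterol and triglyceride events counted only when the grade is worse than the patient's own prestudy fasting grade. In Section 11.5, add the prestudy fasting lipid value to the logistic models for the lipid events. The data are already required by the Section 9.0 calendar, so the cost is one extra table and one extra model term. That term is not entirely free for cholesterol: if the 10% rate applies to the 248 patients with samples, there are about 0.10 × 248 = 24.8, or 25, events. Section 11.5 expects more samples later, which would ease this.
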